### Intervention

The intervention consists of a transfer program (ParTNer-STEPs), offered to the parents from 6 – 18 months before their adolescent child is transferred to adult care (depends on when the participant is recruited before transfer).

ParTNer-STEPs (Parents in Transition – a Nurse-led Support and Transfer Education Program) (figure 1) consist of

- 1) an informative website
- 2) online educational events for parents
- 3) transfer consultations across the paediatric and adult department.

**Figure 1:** Model of the intervention

**Informative website** available for parents from recruitment until follow-up. The website will focus on:

- dissemination of relevant knowledge regarding legal changes, education questions etc
- guidance and tools in relation to how the parents can prepare their adolescent child
- introduction to adult care incl. expectations alignment
- experiences from other parents and adolescents
- Q&A incl. parents' possibility to submit own questions

**Online educational events** offered twice a year as an online webinar with short presentations on different topics. The webinar will not be available for parents after their child has transferred to adult care. The educational events will be focused on:

- Emotions and thoughts during transition
- Adolescence, chronic illness and autonomy
- Knowledge sharing

**Transfer consultations** across the paediatric and adult department. The transition consultations consist of:

- a preparatory consultation (3-6 months before transfer) with the paediatric nurse where focus is on the adolescent's skills, expectations, goals and emotions).
- a farewell consultation with the paediatric nurse (0-3 months before transfer). Focus on relationships, expectations, goals
- a joint consultation (at transfer) where both the paediatrician and the adult physician will be present Focus on cooperation/partnership, relationships, knowledge
- a welcoming consultation with the nurse from the adult care (0-3 months after transfer) Focus on expectations, skills, relationships

## HCP training

All HCP associated with the project will receive training in the intervention before onset. The HCP involved will receive a script for the four consultations, in which the purpose, content, procedure and the subsequent documentation are described. All nurses have or will receive training in developmentally appropriate communication and care.

## Materials and procedures

### Primary outcome

#### *Transition readiness (TR)*

TR measured by the questionnaire Medical self-management and transition readiness. The questionnaire is developed and validated by Williams et al, 2011 (Williams, Sherman et al. 2011). The questionnaire consists of 21 Likert-scaled items assessing the adolescent 's awareness of their health condition and ability to make decisions relevant to their health care needs. All items ask participants to respond on a five item Likert-scale (1=strongly disagree, 2=disagree, 3= neither disagree nor agree; 4=agree and 5= strongly agree). A high score indicates transition readiness. Answered by parents (primary) and adolescent (secondary outcome)

### Main secondary outcome

#### *Allocation of Responsibility (AoR)*

AoR measured by the questionnaire Allocation of Responsibility developed and validated by Bilhartz et al, 2015 (Bilhartz, Lopez et al. 2015) consisting of 13 items. Respondents can choose from one of four answers: 1) parent/guardian takes primary responsibility, 2) responsibility is shared between the parent/guardian and the adolescent, 3) adolescent takes primary responsibility, or Not Applicable or No One Does This. A high score indicates a high level of adolescent responsibility. Answered by parents and adolescents.

### *Uncertainty*

Parental uncertainty measured by the Uncertainty-Scale. The scale is developed and validated by Burström et al., 2019 (Burstrom, Acuna Mora et al. 2019) and measures parental uncertainty during transfer of their child from paediatric to adult care on a linear analogue scale from 0 (not uncertain at all) to 100 (extremely uncertain). A high score indicates a high level of uncertainty. Answered by parents.

### *Health-related quality of life*

Health-related quality of life measured by EQ-5D-5L. The questionnaire comprises five dimensions: mobility, self-care, usual activities, pain/discomfort and anxiety/depression. Each dimension has 5 levels: no problems, slight problems, moderate problems, severe problems and extreme problems. A low score indicates better health-related quality of life. Answered by adolescents

### *Experiences of transfer*

Transfer experiences measured by a self-developed questionnaire with 11 items based on modifiable factors from the SMART transition theory (Schwartz, Brumley et al. 2013). All items ask participants to respond on a five item Likert-scale (1=strongly disagree, 2=disagree, 3= partially agree; 4=agree and 5= strongly agree). A high score indicates a positive experience of transfer. The questionnaire has been content and face validated by parents. Answered by parents.

### Transfer satisfaction

Transfer satisfaction measured by a single question: 'On a scale of 0-100, how satisfied have you been with yours/your child's transition to the adult care?' The scale is a linear analogue scale from 0 (very unsatisfied) to 100 (very satisfied). A high score indicates a high level of satisfaction. Answered by parents and adolescents.

### Data collection and management

Data will be collected through questionnaires at baseline and every six months up to three months after the adolescent's transfer to adult care (Figure 2). Transfer time is registered as the date for the last consultation at paediatric. Questionnaires will be sent out via email or by post based on participants' wishes. The questionnaires will take approximate 10 minutes to complete. All data will be handled confidential and stored in the password protected software REDCap.

**Figure 2** Model of time frame

Questionnaires	Time frame				
	Baseline	6 months	12 months	Transfer	3 months follow-up
Socio-demographic					
Parents	X				
Transition readiness (TR)					
Parents	X	X	X	X	X
Adolescent	X	X	X	X	X
Allocation of Responsibility (AoR)					
Parents	X	X	X	X	X
Adolescent	X	X	X	X	X
The Uncertainty Scale					
Parents	X			X	
EQ-5D-5L					
Adolescent	X			X	X
Experiences of transfer					
Parents					X
Transfer satisfaction					
Parents					X
Adolescent					X

### Statistical analysis

#### Sample size

No previous studies have focused on whether it is possible to increase parents' transition readiness score (TR) by offering them a brief transition program. A previous cross-sectional study found that parents of chronically ill adolescents have an average TR score of 3.12 (SD 0.68) (Williams, Sherman et al. 2011). Based on our clinical experience, advice from the author of the primary outcome questionnaire, and a review of each item in the questionnaire (Medical self-management and transition readiness), we assume that we will be able to increase the parents' TR score in the intervention group with 0.5 points.

We are planning an RCT study with a continuous response variable from an independent control- and intervention group with 1 control(s) per intervention subject. Based on the above-mentioned cross-sectional study we assume the response within each group will be normally distributed with standard deviation 0.68. If the true mean difference in the intervention and control group is 0.50, we will need to include parents of 31 individual adolescents in each group to be able to reject the null hypothesis that the population means of the intervention and control groups are equal with probability (power) 0.80. The Type I error probability associated with this test of this null hypothesis is 0.05. Thus, we need to recruit a total of parents of at least 62 individual adolescents.

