## Abstract

**Background** Transfer from paediatric to adult care for chronically ill adolescents is associated with no-shows and low treatment adherence, as well as anxiety and concerns among parents. Studies show that support for parents results in better transition for both adolescents and parents. The overall goal is to improve chronically ill adolescents' transition to adult care by preparing and supporting the parents. The study aim is to improve parents' (of chronically ill adolescents, 16-18 years) transition readiness by offering them a brief transition program.

**Method** The intervention will be evaluated in a randomised controlled trial (RCT) study over two years. The project will be carried out in four paediatric and adult outpatient clinics at Rigshospitalet, Copenhagen University Hospital, Denmark: nephrology, hepatology, neurology and rheumatology. The intervention consists of a brief transition program (ParTNer-STEPs) targeting parents of chronically ill adolescents aged 16,5 -18 years old. The program consists of three components: 1) a website with information about the adult department and legal changes as well as advice from other parents and young people, 2) online educational events (webinars) for parents and 3) transfer consultations across the paediatric and adult department. Based on a power calculation, we aim to include parents of minimum 62 adolescents. The trial is carried out in 2021-2023, with main measurements at pre-intervention baseline, at transfer, and three months follow-up (post-intervention). Primary outcome: Parents' transition readiness (TR). Secondary outcomes: Adolescents' TR, Allocation of responsibility, Uncertainty and quality of life.

**Discussion** The study will establish whether ParTNer-STEPs is effective in increasing parents' and adolescents' TR, reducing parental uncertainty, and facilitating a shift of treatment responsibility from the parents to the chronically ill adolescent.

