### **Data analysis**

A detailed statistical analysis plan (SAP) will be developed when all participants have completed the final measurement (three months after the completed intervention) in collaboration with statisticians. We plan to include t tests, Pearson's Chi-square test, regression analysis, intention to treat and linear models. Logistic regression analyses will be carried out to describe transition readiness and allocation of responsibility within the intervention group and compare it to the control group's score. Both data from parents and their adolescent child will be analyzed, both as dyads and separately in groups of parents/adolescents. The SAP will be confirmed among all project group members before we will be looking into data.

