### **Missing data, drop out and lost to follow up**

Loss to follow-up and missing data for various reasons is impossible to avoid in randomized trials. We will apply the analysis framework in which missing data related to the intention-to-treat approach depend on making plausible assumptions about the missingness of the data and including all participants in subsequent sensitivity analyses.

1. Attempt to follow up all randomized parents, even if they withdraw from allocated treatment.
2. Perform a main analysis of all observed data that are valid under a plausible assumption about the missingness of the data (i.e., Model-based: data as observed; using linear mixed effects models, assuming that data are 'Missing at Random' [MAR]).
3. Perform sensitivity analyses to explore the effect of departures from the assumption made in the main (#2) analysis (i.e., a non-responder-imputation: using the value at baseline to replace missing data will correspond to a non-responder imputation; these models will potentially be informative even if data are 'Missing Not At Random' [MNAR]).
4. Account for all randomized parents, at least in the sensitivity analyses (covered by #2 and #3 above, plus the corresponding analyses based on the per protocol population).

The interpretation of the corresponding statistical measures of uncertainty of the treatment effect and treatment comparisons will involve consideration of the potential contribution of bias to the P-value, 95% confidence interval, and of the inference in general.

Our primary analysis population will be all parents with available data at baseline, statistically modelled using repeated-measures linear mixed effects models (see above). These models will be valid if data are 'MAR'.

*Sensitivity:* We will analyze all variables, with missing data being handled by multiple imputation techniques.

When the different sensitivity analyses agree, and the analyses on the sensitivity analyses and the main analysis lead to essentially the same conclusions, confidence in the trial results is increased.

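### The 62 adolescents needed in the analysis for 80% power are used as the minimum to recruit, with no allowance for the loss the protocol itself expects

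*Protocol*

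**What the plan says.** The Sample size section of the protocol plans a comparison of two independent group means with 1:1 allocation, a difference of 0.50, an SD of 0.68 and power 0.80. On the error rate it says "The Type I error probability associated with this test of this null hypothesis is 0.05". The result is that "we will need to include parents of 31 individual adolescents in each group", and the section ends: "Thus, we need to recruit a total of parents of at least 62 individual adolescents". The Abstract repeats the figure as the inclusion target: "we aim to include parents of minimum 62 adolescents".

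The section on missing data begins: "Loss to follow-up and missing data for various reasons is impossible to avoid in randomized trials". It deals with loss only in the analysis, through a repeated-measures linear mixed model valid under missing at random, with imputation as sensitivity analysis. On who is analysed it says: "Our primary analysis population will be all parents with available data at baseline".

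No section gives an expected loss rate or a margin for loss.

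**The concern.** A two-sample power calculation counts units with an observed outcome. The protocol carries that count over unchanged to the number recruited, which is correct only if almost every family completes. Its own missing-data section says that will not happen. Exposure to loss is also long: families enter 6 to 18 months before transfer and are followed by questionnaire until three months after it, which is roughly 9 to 21 months.

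The 0.80 figure is the only justification given for the size of the trial. A reader will take 62 recruited to mean 80% power for the stated comparison, and will judge a null result against that figure.

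**Working it through.** **Inputs (Protocol, Sample size).** Difference δ = 0.50, SD σ = 0.68, α = 0.05, power 0.80, allocation 1:1. Sidedness is not stated. The null hypothesis is equality of means, so I take the test as two-sided.

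**Step 1: reproduce 31 per group.** The standardised difference is 0.50 / 0.68 = 0.735. The normal approximation n = 2(z₀.₉₇₅ + z₀.₈₀)²(σ/δ)² = 2 × (1.960 + 0.842)² × 1.36² ≈ 29.03 rounds up to 30. The exact calculation with the non-central t distribution gives 30.03, which rounds up to 31. A one-sided test would need 24. The protocol's 31 is therefore the exact two-sided t-test requirement, with nothing added for loss.

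**Step 2: power of the stated comparison by number analysed.** With n₁ and n₂ analysed, the non-centrality parameter is δ / (σ√(1/n₁ + 1/n₂)) with n₁ + n₂ − 2 degrees of freedom. For 31 + 31 it is 0.50 / (0.68 × √(2/31)) = 2.895, the critical value on 60 df is 2.000, and power is 0.813.

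| Total analysed of 62 recruited | Power |
|---|---|
| 62 | 0.813 |
| 61 | 0.806 |
| 60 | 0.7997 |
| 59 | 0.793 |
| 58 | 0.786 |
| 56 | 0.771 |
| 50 | 0.722 |

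The 80% level is reached or just missed at 60 analysed, so the room for loss is about one family per group. A family counts as lost when no parent of that adolescent gives the outcome.

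**Step 3: by assumed loss rate.** The protocol gives no rate, so these are illustrations with 31 × (1 − loss) analysed per group.

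| Assumed loss | Analysed per group | Power | Difference detectable with 80% power |
|---|---|---|---|
| 0% | 31 | 0.813 | 0.49 |
| 5% | 29.45 | 0.792 | – |
| 10% | 27.9 | 0.769 | 0.52 |
| 20% | 24.8 | 0.718 | 0.55 |

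**Step 4: can the planned mixed model make this up?** The protocol gives no correlations, so I assumed a range: baseline with each later visit 0.2 to 0.5, and transfer with three months 0.3 to 0.8. The calculation uses generalised least squares information for baseline, transfer and three months, with a common baseline mean in both groups and degrees of freedom from families with complete data. The 6- and 12-month visits are left out.

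| Contrast | What lost families still provide | 10% loss | 20% loss |
|---|---|---|---|
| Three months | Baseline and transfer | 0.79 to 0.89 | 0.74 to 0.87 |
| Transfer | Baseline and transfer | 0.83 to 0.91 | 0.83 to 0.91 |
| Either | Baseline only | – | 0.74 to 0.83 |

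The results fall on both sides of 80%. Which side applies depends on the correlations, the pattern of loss and the time point. The Abstract names two main measurements after baseline, transfer and three months. Neither the sample-size section nor the missing-data section says which one carries the primary comparison.

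**The case against.** The strongest reply is that the figures of 77% and 72% belong to a complete-case t test, whereas the main analysis is a repeated-measures mixed model on all parents with baseline data. Step 4 shows that this model can hold 80% or more at 20% loss. The protocol also schedules up to five readiness measurements, and the two omitted from Step 4 could add information. It intends to follow all randomised parents even after withdrawal. All of this stands, and it is why no shortfall in the main analysis is claimed. It does not rescue the sentence as written: the sample-size section calculates a plain two-group comparison and claims no gain from repeated measures. An analysis valid under missing at random does not by itself restore lost information.

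A second point is that more than one parent per family may answer. Suppose two parents answered in every family and the family mean were analysed. At 20% loss, power would be about 0.83 if the correlation between parents were 0.5 and about 0.79 if it were 0.7. This is a possible offset, but the protocol neither states how many parents answer nor uses it.

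Third, 62 is worded as a floor, so more may be recruited. That is true, but permission to exceed a floor is not a planned margin.

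Fourth, the effect is modest at low loss, and the assumed 0.50 matters more: a true difference of 0.45 gives 73% power with no loss at all. That is fair on scale, but it is a separate uncertainty and leaves even less slack.

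Finally, the matter might be left to the SAP. The protocol says "A detailed statistical analysis plan (SAP) will be developed when all participants have completed the final measurement", which is after recruitment has ended. This is a side issue, since the basis for recruitment belongs in the protocol and can be amended there.

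**Conclusion.** The point holds. The figure of 31 per group is correct as the number to be analysed and wrong as the number to recruit for the stated power. For the comparison the protocol describes, 62 recruited gives 80% only with about two losses or fewer in total. Power falls to 79%, 77% and 72% at assumed losses of 5%, 10% and 20%.

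The t-test figures rest on the protocol's own difference and SD and a two-sided test. The loss rates, and everything about the mixed model, are assumptions. Whether the main analysis would fall below 80% cannot be determined from the protocol. This should be fixed because the trial's size rests on the figure, but it does not show that the trial will fail.

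**What to change.** In the Sample size section, keep 62 and add one or two sentences. They should say that power 0.80 refers to about 31 analysed adolescents per group, give the expected loss, and give the power of the stated comparison at that loss (for example 79% at 5%, 77% at 10% or 72% at 20%). If the team wants to keep 80% by relying on the mixed model, it should restate the power for that model with the assumed correlations, the loss pattern and the time point of the primary contrast.

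The cost is a slightly less favourable stated power and a commitment to an expected loss rate. The number recruited, the test and the analysis do not change.

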### **Data analysis**

A detailed statistical analysis plan (SAP) will be developed when all participants have completed the final measurement (three months after the completed intervention) in collaboration with statisticians. We plan to include t tests, Pearson's Chi-square test, regression analysis, intention to treat and linear models. Logistic regression analyses will be carried out to describe transition readiness and allocation of responsibility within the intervention group and compare it to the control group's score. Both data from parents and their adolescent child will be analyzed, both as dyads and separately in groups of parents/adolescents. The SAP will be confirmed among all project group members before we will be looking into data.

### **Missing data, drop out and lost to follow up**

Loss to follow-up and missing data for various reasons is impossible to avoid in randomized trials. We will apply the analysis framework in which missing data related to the intention-to-treat approach depend on making plausible assumptions about the missingness of the data and including all participants in subsequent sensitivity analyses.

1. Attempt to follow up all randomized parents, even if they withdraw from allocated treatment.
2. Perform a main analysis of all observed data that are valid under a plausible assumption about the missingness of the data (i.e., Model-based: data as observed; using linear mixed effects models, assuming that data are 'Missing at Random' [MAR]).
3. Perform sensitivity analyses to explore the effect of departures from the assumption made in the main (#2) analysis (i.e., a non-responder-imputation: using the value at baseline to replace missing data will correspond to a non-responder imputation; these models will potentially be informative even if data are 'Missing Not At Random' [MNAR]).
4. Account for all randomized parents, at least in the sensitivity analyses (covered by #2 and #3 above, plus the corresponding analyses based on the per protocol population).

The interpretation of the corresponding statistical measures of uncertainty of the treatment effect and treatment comparisons will involve consideration of the potential contribution of bias to the P-value, 95% confidence interval, and of the inference in general.

Our primary analysis population will be all parents with available data at baseline, statistically modelled using repeated-measures linear mixed effects models (see above). These models will be valid if data are 'MAR'.

*Sensitivity:* We will analyze all variables, with missing data being handled by multiple imputation techniques.

When the different sensitivity analyses agree, and the analyses on the sensitivity analyses and the main analysis lead to essentially the same conclusions, confidence in the trial results is increased.

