## Participants

### Eligibility criteria

Participants are parents, stepparents or guardians (will subsequently only be referred to as parents) of chronically ill adolescents affiliated with the four paediatric outpatient clinics. The adolescents will participate in

the intervention and contribute with outcome measurements. Parents who meet the following criteria will be invited to participate in the study. *Inclusion criteria:* Parents to chronically ill adolescents who 1) are aged 16.5-17.5 years (can be recruited up to six months before transfer), 2) have been diagnosed for minimum six months, 3) have regular check-ups at the Department of Paediatrics and Adolescent Medicine's nephrology, hepatological, neurological and rheumatological outpatient clinics at Rigshospitalet, Denmark, 4) will be transferred to an adult hospital department and 5) are mentally and cognitively able to take responsibility for their own treatment. *Exclusion Criteria:* 1) Parents who do not read and speak Danish and 2) Parents of adolescents who will be transferred to their family doctor at the age of 18 year.

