### Randomisation

[figure not shown]
Randomisation will be conducted after screening and written consent of parents. Randomisation will be conducted by computer-generated (REDCap) random numbers as a dyad (adolescent and parents) with a ratio of 1:1 (using algorithm to stratify by the four outpatient's clinic). The dyads will be randomised into two groups 1) receive the intervention (standard care plus ParTNer-STEPs until their child's transfer to adult care) or 2) standard care (control group). Once the database has defined a dyad's allocation, no changes can be made. Those randomised to the intervention arm will then receive access to the intervention materials.

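### Families are randomised and counted, but the primary analysis population is defined as parents, with no rule for two parents of one adolescent

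*Protocol*

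**What the plan says.** Below, a family means one adolescent and his or her participating parents.

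- **Randomisation** gives one allocation per family: "Randomisation will be conducted by computer-generated (REDCap) random numbers as a dyad (adolescent and parents) with a ratio of 1:1". The bracket uses the plural for the parents.
- **Sample size** counts the same unit: "we will need to include parents of 31 individual adolescents in each group". It uses a formula for independent groups.
- **Eligibility criteria** sets no limit per adolescent: "Participants are parents, stepparents or guardians". The Primary outcome section has parents answer the readiness questionnaire and names no index parent.
- **Missing data, drop out and lost to follow up** changes the unit. Item 1 reads "Attempt to follow up all randomized parents, even if they withdraw from allocated treatment" and item 4 "Account for all randomized parents, at least in the sensitivity analyses". The primary population and model follow: "Our primary analysis population will be all parents with available data at baseline, statistically modelled using repeated-measures linear mixed effects models".
- **Data analysis** comes nearest to family structure: "Both data from parents and their adolescent child will be analyzed, both as dyads and separately in groups of parents/adolescents". It does not say which of these analyses is primary, and it concerns parent with adolescent, not two parents of one adolescent.

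**The concern.** The treatment comparison is randomised between families. Two parents of one adolescent share one allocation and rate the same young person's readiness, so a positive correlation between their scores is plausible. A repeated-measures model with parents as subjects handles the correlation between visits of one parent. It does not by itself handle the correlation between two parents.

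If both parents respond in some families and the model stops at the parent level, the primary standard error is too small, the confidence interval too narrow, and the type I error above the 0.05 used in the Sample size section. The population and model are fixed in the protocol itself, so an analysis plan that follows the text literally would carry the parent unit forward.

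**Working it through.** **1. The plan's own figure.** Inputs from Sample size: difference 0.50, SD 0.68, power 0.80, type I error 0.05, ratio 1:1. A two-sided two-sample t-test needs n = 30.03 per arm, rounded up to 31. Power is 79.97% at 30 and 81.3% at 31. Sidedness is not stated, but a one-sided test would need only 23. The stated 31 therefore reproduces, as a count of families with one independent value each.

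**2. Effect of ignoring family, no baseline adjustment.** The documents give neither the share of families with two responses (p) nor the co-parent correlation at the same visit (ICC). Both are assumptions here. With F families in an arm there are N = F(1 + p) parents, and the variance of the arm mean is

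σ²·[F(1 − p) + F·p·(2 + 2·ICC)] / N².

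Dividing by the naive σ²/N gives

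- design effect: deff = 1 + 2·p·ICC / (1 + p)
- true type I error of the nominal 5% test = 2·[1 − Φ(1.96 / √deff)]
- understatement of the standard error = 1 − 1/√deff

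Example: p = 0.25, ICC = 0.3 gives deff = 1 + 0.15/1.25 = 1.12, type I error 6.4%, standard error 5.5% too small.

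| p | ICC 0.1 | ICC 0.3 | ICC 0.5 | ICC 0.7 | SE too small by |
|---|---|---|---|---|---|
| 0 | 5.0% | 5.0% | 5.0% | 5.0% | 0% |
| 25% | 5.5% | 6.4% | 7.4% | 8.3% | 2–12% |
| 50% | 5.8% | 7.4% | 9.0% | 10.6% | 3–17% |
| 100% | 6.2% | 8.6% | 10.95% | 13.3% | 5–23% |

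**3. With baseline adjustment.** If co-parents share the stable level and the visit-to-visit changes alike, the table is unchanged. If they share only the stable level, adjustment removes part of the correlation. Let r be the within-parent correlation between visits and k the number of follow-up visits averaged. Then

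- residual variance: V = [1 + (k − 1)r]/k − r²
- residual co-parent correlation = ICC·(1 − r)² / V

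Take r = 0.6 (an assumption; ICC then cannot exceed 0.6) and ICC = 0.5, so ICC·(1 − r)² = 0.5 × 0.16 = 0.08. The time-frame table lists up to four follow-up readiness assessments, so k runs from 1 to 4.

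| k | V | Residual correlation | p = 25% | p = 50% | p = 100% |
|---|---|---|---|---|---|
| 1 | 0.64 | 0.125 | 5.6% | 6.0% | 6.5% |
| 2 | 0.44 | 0.182 | 5.8% | 6.4% | 7.1% |
| 4 | 0.34 | 0.235 | 6.1% | 6.8% | 7.8% |

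Simulation of selected cases, unadjusted and with a baseline covariate (k = 2 where only the stable level is shared), used 20,000 null trials each, 31 families per arm and complete data. It agreed with these formulas within 0.4 percentage points; the Monte Carlo standard error is about 0.2 points.

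**4. Interval width and power at 31 families per arm (SD 0.68, no baseline adjustment).**

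- One value per family: SE = 0.68·√(2/31) = 0.173, 95% half-width 0.345.
- p = 25%, ICC 0.3: N = 38.75 parents per arm. Ignoring family, SE = 0.154 and half-width 0.308. With family, SE = 0.154·√1.12 = 0.163 and half-width 0.327.
- p = 100%, ICC 0.5: half-width 0.242 ignoring family, 0.299 with family.
- Power: 81.3% with one value per family. With two parents in every family and ICC 0.5, the SD of a family mean is 0.68·√0.75 = 0.589 and power is 90.8%.

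**The case against.** The best defence is that the protocol often uses parents as a collective word for the parent side of a family. The sample size speaks that way, a dyad has two sides, and the time-frame table has one parent row per instrument. On that reading the missing-data section means the parent side of each randomised family, the units agree, and nothing is inflated. No section says that both parents return a questionnaire. This stands as a possible reading, but the text does not secure it: eligibility sets no limit, and the randomisation bracket uses the plural.

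A second defence is that random-effects structure belongs in the SAP. That is fair for detail. Here, however, the protocol itself names the primary population and does so in a unit that differs from its randomisation and sample size.

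Three stronger readings are tempting, and the documents do not support them:

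- *That the model is wrong.* A linear mixed model can hold a family term. None is excluded, and no section says co-parents are treated as independent.
- *That the trial is too small.* The 31 per arm is correct for families, and second parents add information if their correlation is modelled.
- *That the unit will be chosen after seeing results.* The SAP is to be written after the last measurement, but the protocol also says: "The SAP will be confirmed among all project group members before we will be looking into data".

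**Conclusion.** The point holds as an unreconciled unit of analysis that should be fixed, not as a proven error. The size is conditional. There is no inflation if each family gives one response. If a quarter of families give two, nominal 5% becomes 5.5–8.3% without baseline adjustment. The 13.3% extreme needs two responses from every family, a co-parent correlation of 0.7, no family term, and either no baseline adjustment or co-parents who share visit-to-visit changes as fully as their stable level. With adjustment and only the stable level shared, about 5.6–7.8% is the relevant range for the assumptions in step 3. Confidence is medium, because the share of two-parent families and all the correlations are assumed.

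**What to change.** In the missing-data section, state that the family (adolescent) is the randomised unit and the unit of inference. State also that all participating parents enter the primary mixed model with a family random intercept: parent nested in family, visits nested in parent. Name family-clustered standard errors as the fallback if that model does not converge, which could happen if few families give two responses.

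Keep the commitment in item 1 to follow up every participating parent. Rewording it to families alone could let a family count as followed when only one parent responds.

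Any analysis of one index parent per family should be supportive and use a parent designated before allocation. Choosing the parent whose baseline questionnaire arrives first would not be safe: the abstract places baseline before the intervention, but the Randomisation section does not place it before allocation, so the arm could influence who answers first.

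The cost is one or two sentences, with no extra participants or data. The interval is somewhat wider than when family is ignored: half-width about 0.33 instead of 0.31 at p = 25% and ICC 0.3. In both cases worked above it stays below the 0.345 implied by one value per family, a figure derived here and not stated in the protocol.
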